### **10.9 Dose Adjustments, Infusion Delays, and Missed Doses**

Missed doses of CB-839 should be skipped. If a patient forgets to take a dose of study drug and he/she is outside of the allotted window period ( $\pm 6$  hr), he/she should be instructed to skip that dose and NOT to take extra study drug at the next administration.

Subjects may be dosed with nivolumab no less than 12 days from the previous dose. If a subject cannot receive the 2nd nivolumab dose of the cycle within the 28 day period it will be omitted and the next dose received will be considered Day 1 of the next cycle.

### **10.10 Discontinuation of Treatment and Withdrawal of Patients**

The reasons a patient may discontinue or be withdrawn from the study include, but are not limited to, adverse events, disease progression, patient request, Investigator decision, protocol violation, patient noncompliance, and study termination by the Sponsor.

When a patient discontinues or is withdrawn from study, the Investigator will notify the Sponsor (or designee) and should perform all End of Treatment and follow up procedures as indicated in the [Schedule of Study Assessments](#) after discontinuation of study drug.

## 11.0 TEST ARTICLE/STUDY DRUG

### 11.1 Test Article Administration

#### CB-839

Test article (CB-839) will be administered orally using a capsule (200 mg per capsule) or tablet (200 mg per tablet) formulation. CB-839 will be administered only to patients who have signed and dated an Informed Consent Form. CB-839 will be administered on Days 1 through 28 of each 28-day cycle and should be taken orally using the number of capsules or tablets directed in the Pharmacy Manual. CB-839 dosing will not be adjusted for body weight or surface area.

The first CB-839 dose of the day will be administered immediately after breakfast. The evening/second dose should be taken with a meal approximately 12 hr ( $\pm$  2 hr) after the morning dose.

On PK days (Cycle 1 Days 1 and 15, Cycle 2 Day 1 and Cycle 3 Day 1) patients should be instructed NOT to take their morning dose of CB-839 at home. On PK days, patients will have all predose procedures performed, take their dose of CB-839 with food then receive nivolumab. The time of dosing will be recorded in the clinic. The evening dose will be self-administered by the patient after all postdose activities have been completed. On non-PK collection days, patients will administer CB-839 per their usual administration schedule.

Patients who vomit their CB-839 dose should be instructed NOT to make up that dose and to report the frequency of vomiting occurrences associated with study drug administration to the site. Patients who report  $\geq$  3 incidences of vomiting associated with study drug administration will have a blood sample drawn for an unscheduled PK analysis.

Nivolumab: Nivolumab will be administered at a flat dose of 240 mg IV infusion over 60 min on Days 1 and 15 of each 28-day cycle. Nivolumab (Opdivo®) is supplied by Calithera as a

10 mg/mL solution for infusion following dilution. Please refer to the [nivolumab package insert](#) for specific instructions on nivolumab administration.

## 11.2 Packaging and Labeling

CB-839 HCl Capsules (200 mg) and CB-839 HCl Tablets (200 mg) are manufactured, packaged, and labeled according to current Good Manufacturing Practices (cGMP). For additional information, please refer to the Pharmacy Manual.

Nivolumab is available in single use vials containing 40 mg/4 mL or 100 mg/10 mL. Please refer to the [nivolumab package insert](#) for specific instructions on packaging and labeling.

## 11.3 Storage and Stability

### CB-839

CB-839 HCl Capsules and Tablets will be stored at the clinical site, as indicated on the study drug label, i.e. room temperature, between 15°-30°C (59°-86°F).

Patients will be requested to store the test article at the recommended storage conditions noted on the label, out of the reach of children or other cohabitants.

### Nivolumab

Nivolumab vials should be stored under refrigeration at 2°C - 8°C (36°F - 46°F). Protect from light by storing in the original package until time of use. Do not freeze or shake. For procedures for the proper handling, storage, preparation and administration of nivolumab, please refer to the [nivolumab package insert](#).

## 11.4 CB-839 Accountability, Reconciliation, and Return

On Day 1 of Cycle 1, patients will be provided with enough CB-839 to last until their next clinic visit. Patients will return on Day 1 of each cycle thereafter and will receive a 28 day supply of CB-839; the number of capsules/tablets remaining from the previous visit will be counted and recorded.

The Investigator or designee must maintain an accurate record of dispensing the study drug in a Drug Accountability Log, a copy of which must be given to the Sponsor at the end of the study. The Drug Accountability Log will record the study drugs received, dosages prepared, time prepared, doses dispensed, and doses and/ or bottles destroyed. The Drug Accountability Log will be reviewed by the field monitor during site visits and at the completion of the study.

If evidence of tampering is observed, notify the Sponsor and return the questionable CB-839 shipment with the appropriate for to the contract distribution center. Returned and unused CB-839 test article may also be destroyed and documented at the investigative site in accordance with approved site/institution standard operating procedures.

### **11.5 Test Article Compliance**

At each clinic visit, patients will be asked to return any unused CB-839 test article and will be questioned about their test article compliance. The number of remaining capsules/tablets will be recorded in the drug accountability log. Significant non-compliance (missing > 60% of the study drug for reasons other than documented AE) must be reported to the monitor.

Missed doses of CB-839 should be skipped. If a patient forgets to take a dose of study drug and he/she is outside of the allotted window period ( $\pm 6$  hr), he/she should be instructed NOT to take extra study drug at their next administration.

### **12.0 MEASURES TO MINIMIZE/AVOID BIAS**

Each patient will be assigned a unique number and will keep this number for the duration of the study. Patient numbers will not be reassigned or reused for any reason. Patients should be identified to the Sponsor only by their assigned number, initials, date of birth, and sex. The Investigator must maintain a patient master log.

### **13.0 SAFETY EVALUATIONS**

Routine safety and tolerability will be evaluated from the results of reported signs and symptoms, scheduled physical examinations, vital sign measurements, 12-lead ECGs (including QTcF intervals), and clinical laboratory test results.

More frequent safety evaluations may be performed if clinically indicated or at the discretion of the Investigator. All AEs will be recorded from the time the patient receives the first dose of study drug up to 28 days after the last dose.

### 13.1 Physical Examination

Complete physical examinations will be performed by a licensed physician (or physician's assistant or nurse practitioner) at Screening and End of Treatment. Symptom-directed physical exam are required as clinically indicated. Please refer to the Schedule of Study Assessments ([Attachment 1](#)).

### 13.2 Vital Signs

Vital signs (blood pressure, respiratory rate, pulse rate, and temperature) will be obtained in the sitting position. All patients should be sitting for 3-5 min prior to obtaining vital signs. On the day of nivolumab infusion, vital signs will be obtained pre-infusion and within 30 min of the end of infusion. Vital signs should be collected  $\pm$  5 min from the scheduled times noted above.

### 13.3 Electrocardiograms

Patients should rest in the supine position for at least 5 min before the 12-lead ECG recording is started. ECG recordings must be performed using a standard, high-quality, high-fidelity electrocardiograph machine equipped with computer-based interval measurements.

For safety monitoring purposes, the ECG must be reviewed, signed, and dated promptly by a qualified physician (or qualified physician's assistant or nurse practitioner) and any clinically important finding recorded on the appropriate eCRF. The Investigator is responsible for providing the interpretation of all ECGs. The results will include heart rate (HR), R-R interval (RR), PR interval, QRS interval, QT interval, and QTcF interval. The corrected QT interval will be corrected for respiratory rate according to the following formula:

$$\text{Fridericia's formula: } QTcF = QT/RR^{0.33}$$

### 13.4 Safety Laboratory Determinations

Laboratory evaluations will be performed as noted in the [Schedule of Study Assessment](#).

## 14.0 BIOMARKER AND PHARMACODYNAMIC SAMPLES

### 14.1 Archival Tumor Biopsy Samples

Archival surgical samples and biopsy specimens must be provided from all patients on study who have archival tissue available. Samples should be collected and shipped according to instructions provided in the Laboratory Manual.

### 14.2 Predose and Postdose Tumor Biopsies

Tissue for exploratory biomarker assessment will be obtained from fresh tumor biopsies performed prior to the initiation of treatment (“predose”) and while on treatment (“postdose”). These samples will be used for a) the analysis of gene expression levels and b) for immunohistochemical/immunofluorescence analysis. Tissue may also be used for the evaluation of additional exploratory biomarkers that are not pre-specified in this protocol based upon new scientific literature and/or preclinical data.

Predose biomarkers will be used primarily to identify potential biomarkers that are predictive of response to therapy. In order to assess the impact of CB-839 on the pharmacodynamic effects of nivolumab, mandatory pre- and-post treatment biopsies will be obtained from patients who progressed on nivolumab or pembrolizumab in the immediate prior line of therapy (Cohort 2, 4, and 5). [Table 14.2-1](#) below indicates which patients are required to have tumor biopsies.

**Table 14.2-1: Summary of Tumor Biopsy\* Collections for Patients**

	Cohorts	Predose Biopsy	Postdose Biopsy C2D1 (± 1 week)**
Phase 1: Dose Escalation	600 mg CB-Nivo 800 mg CB-Nivo (400 mg CB-Nivo if required)	Optional	Optional
	Backfill patients	Mandatory 4-6 cores	Mandatory 4-6 cores
Phase 2: Cohort Expansion	Cohort 1: ccRCC - Checkpoint inhibitor naïve	Mandatory 4-6 cores (Archival accepted if taken <1 yr)	Optional
	Cohort 2: ccRCC - Nivo in most recent line of therapy ("add-on")	Mandatory 4-6 cores	Mandatory 4-6 cores
	Cohort 3: ccRCC - Any prior anti-PD-1	Mandatory 4-6 cores	Optional
	Cohort 4: Melanoma	Mandatory ***	Mandatory***
	Cohort 5: NSCLC	Mandatory 4-6 cores	Mandatory 4-6 cores
	Cohort 6: Melanoma	Mandatory ***	Optional

\*Biopsies are not required if deemed unsafe or technically unfeasible. Discuss with Medical Monitor.

\*\*The timing of the post dose biopsy will be subject to clinical feasibility and if this window cannot be met, this can be discussed with the Medical Monitor.

\*\*\* Excisional or punch biopsies are preferred. Core biopsies are acceptable.

Biopsies will be processed and shipped according to the instructions provided in the Laboratory Manual. Enrollment of patients for whom tumor biopsy is not safe or feasible to perform may be considered based on discussion with the Medical Monitor.

Optional tumor biopsies for exploratory biomarker assessment may be collected at any point on this study with patient consent (e.g., progression biopsies).

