#### **6.3.2.4 Cohort 4: Melanoma patients with disease progression while receiving an anti-PD-1 therapy in their most recent line of therapy**

This cohort will enroll melanoma patients with radiological disease progression (per Investigator assessment) while receiving an anti-PD-1/PD-L1 agent as monotherapy or in a combination regimen to treat advanced/metastatic melanoma in the most recent line of therapy. There must be  $\leq 8$  weeks elapsed between last dose of anti-PD-1/PD-L1 and C1D1 of the CX-839-004 trial. The intent of this cohort is to convert progressing disease to responding disease by the addition of CB-839 to ongoing anti-PD-1/PD-L1 therapy. Because this patient population has documented disease progression on anti-PD-1/PD-L1 therapy at study start, the likelihood of a response to nivolumab monotherapy is extremely low and any activity can be confidently attributed to the addition of CB-839. Patients on anti-PD-1/PD-L1 agent other than nivolumab will switch to nivolumab for treatment on this study. The primary endpoints of Cohort 4 will be ORR and DOR as determined by an Independent Radiology Committee (IRC). Pre- and post-dose biopsies will be collected from all patients enrolled into the Expansion phase of Cohort 4 (so long as deemed safe and technically feasible to biopsy) in order to demonstrate a pharmacodynamic effect of CB-839 in the context of PD-1 inhibition and to correlate efficacy with potential predictive biomarkers ([Section 14.2](#)).

The original study design with 24 patients tested the null hypothesis that ORR of CB-839 + nivolumab was  $\leq 5\%$  versus the alternative of  $\geq 20\%$  with an alpha level of 0.1 and power of

80%. Per study design, 9 patients would be enrolled in Stage 1 and 1 responder would trigger enrollment of an additional 15 patients in Stage 2; while 3 responders out of 24 total patients would lead to formal rejection of the null hypothesis. To date there have been 3 responding patients (including one complete response and 2 deep partial responses of -73% and -47%), all confirmed responses on repeat scan  $\geq 4$  weeks after initial response, in 16 evaluable patients. Notably, per protocol eligibility, all of these patients were experiencing disease progression on PD-1/PD-L1 inhibitor therapy in the immediate prior line of therapy strongly suggesting that the response was the result of the addition of CB-839.

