#### 6.4 Inclusion Criteria

1. Patients must have a histological or cytological diagnosis of metastatic cancer or locally advanced cancer that is not amenable to local therapy. Additional criteria specific to different Cohorts of the study are provided below.
2. Ability to provide written informed consent in accordance with federal, local, and institutional guidelines
3. Age  $\geq$  18 years
4. Eastern Cooperative Oncology Group (ECOG) Performance Status of 0-1
5. Life Expectancy of at least 3 mo
6. Patient must have adequate organ function as indicated by the following laboratory values:

Test	Value
Absolute neutrophil count (ANC)	$\geq 1,500$ /mcL
Total white blood cell (WBC) count	$\geq 2,000$ /mm 
Platelets	$\geq 100,000$ / mcL
Hemoglobin	$\geq 9$ g/dL
Serum creatinine	$\leq 1.5$ X upper limit of normal (ULN)
Serum total bilirubin	$\leq 1.5$ X ULN OR
Direct bilirubin (for patients with Gilbert Syndrome and total bilirubin levels $>1.5$ ULN)	$\leq$ ULN
AST (SGOT) and ALT (SGPT)	$\leq 2.5$ X ULN

International Normalized Ratio (INR) or Prothrombin Time (PT)	$\leq 1.5 \times \text{ULN}^*$
Activated Partial Thromboplastin Time (aPTT)	$\leq 1.5 \times \text{ULN}$

\* Does not apply to patients receiving therapeutic warfarin

7. Measurable Disease: At least one tumor lesion/lymph node that meets the RECIST v1.1 criteria for measurable disease
8. Female patients of childbearing potential must have a negative serum or urine pregnancy test within 3 days prior to the first dose of study drug and agree to use dual methods of contraception if sexually active during the study and for a minimum of 3 mo following the last dose of study drug. Post-menopausal females (> 45 years old and without menses for > 1 year) and surgically sterilized females are exempt from these requirements. Male patients must use an effective barrier method of contraception during the study and for a minimum of 3 mo following the last dose of study drug if sexually active with a female of childbearing potential.
9. Resolution of all treatment-related toxicities from any previous cancer therapy (including radiation and surgery) to  $\leq$  Grade 1 or to values within those required for eligibility on this study prior to the first dose of study treatment.
  - a. Exceptions include alopecia, anemia, or endocrinopathies managed by hormone replacement

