## 10.3 Cycle 2 and all subsequent cycles

Patients will return to the clinic and undergo the following procedures:

- AE monitoring
- Recording of concomitant medications

- Vital signs and weight
- Symptom-directed physical exam
- Clinical laboratory values (hematology, coagulation, serum chemistry and urinalysis)
- ECOG performance status evaluation
- Plasma sample for collection for biomarker analysis taken prior to dosing on Cycles 2 and 3 Day 1
- Whole blood sample collection for biomarker analysis taken prior to dosing on Cycles 2 and 3 Day 1
- Administration of CB-839 and nivolumab
  - Patients should be instructed not to eat breakfast prior to their clinic visit on Cycle 2 Day 1 and Cycle 3 Day 1. Patients will undergo the predose assessments prior to receiving the nivolumab infusion or eating breakfast and receiving the CB-839 dose. The 2nd dose of CB-839 will be self-administered by the patient per dosing instructions after all study procedures have been completed.
- A postdose tumor biopsy will be obtained from all patients in Phase 1 backfill cohorts, Phase 2- Cohorts 2, 4, and 5 on Cycle 2 Day 1 only ( $\pm$  1 week). Coagulation tests must be performed and evaluated within 72 to 24 hr prior to all biopsy procedures.
- Radiographic evaluation (e.g., diagnostic CT or MRI) of tumor burden will occur approximately every 8 weeks. The same method of evaluation should be used throughout the course of the study. The scans and redacted reports will be collected and sent to a central reader for exploratory evaluation.

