#### 10.4 Other Schedules and Procedures

Radiographic evaluation of tumor burden (e.g., diagnostic CT/MRI) will occur at Screening and approximately every 8 weeks from Cycle 1 Day 1 and as clinically indicated.

Optional tumor biopsies may be obtained at variable time points as advised by the Investigator.

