**ATTACHMENT 2: PHARMACOKINETIC AND BIOMARKER SAMPLING SCHEDULE**

Detailed instructions on sample collection and shipment can be found in the Laboratory Manual.

Study Day	Time point (Relative to CB-839 Dosing)	Phase 1 only PK/ Biomarker	Phase 2 only PK/ Biomarker	Phase 1 and Phase 2 Biomarker: RNA	Phase 1 and Phase 2 Biomarker: CPT	Phase 1 and Phase 2 Biomarker: TCR^6	Phase 1 and Phase 2 Tumor Biopsy
Screening							4-6 Cores
Cycle 1 Day 1	Predose	3 mL	3 mL	5 mL	32 mL	3 mL	
Cycle 1 Day 1	0.5 hr	3 mL					
Cycle 1 Day 1	1 hr	3 mL					
Cycle 1 Day 1	2 hr	3 mL					
Cycle 1 Day 1	4 hr	3 mL					
Cycle 1 Day 1	6 hr	3 mL					
Cycle 1 Day 1	8 hr	3 mL					
Cycle 1 Day 15	Predose	3 mL	3 mL	5 mL		3 mL	
Cycle 1 Day 15	0.5 hr	3 mL					
Cycle 1 Day 15	1 hr	3 mL					
Cycle 1 Day 15	2 hr	3 mL					
Cycle 1 Day 15	4 hr	3 mL					
Cycle 1 Day 15	6 hr	3 mL					
Cycle 1 Day 15	8 hr	3 mL					
Cycle 2 Day 1	Predose	3 mL	3 mL	5 mL	32 mL		4-6 Cores
Cycle 3 Day 1	Predose	3 mL	3 mL	5 mL	32 mL	3 mL	
Total sample collected		48 mL blood	12 mL blood	20 mL blood	96 mL blood	9 mL blood	

1. Where applicable, the collection window is  $\pm 15$  minutes. The actual sample collection time will be entered in the EDC.
2. Blood samples will be collected for all patients enrolled in the Phase 1 Dose Escalation.
3. Blood samples will be collected from all patients enrolled in the Phase 2 Dose Expansion
4. 2.5 mL of whole blood will be collected in to two Paxgene Blood RNA tubes.

5. 8 mL of whole blood will be collected in to four Vacutainer CPT cell preparation tubes with sodium heparin. The CPT tubes will be centrifuged at room temperature for 30 min at 1800 RCF (relative centrifugal force).
6. 3mL of whole blood will be collected in to 1 EDTA tubes. The EDTA tubes should be placed in -80°C storage.
7. At least 4-6 tissue cores will be collected from patients. 14-18 gauge needle core biopsies are preferred however, 20 gauge needles can be used at the discretion of the radiologist and treating physician. For melanoma patients, excisional or punch biopsies are preferred.

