### Special notes on the assessment of target lesions

**Lymph nodes:** Lymph nodes identified as target lesions should always have the actual short axis measurement recorded (measured in the same anatomical plane as the baseline examination), even if the nodes regress to below 10 mm on study. This means that when lymph nodes are included as target lesions, the ‘sum’ of lesions may not be zero even if complete response criteria are met, since a normal lymph node is defined as having a short axis of < 10 mm. Case report forms or other data collection methods may therefore be designed to have target nodal lesions recorded in a separate section where, in order to qualify for CR, each node must achieve a short axis < 10 mm. For PR, SD, and PD, the actual short axis measurement of the nodes is to be included in the sum of target lesions.

**Target lesions that become ‘too small to measure’:** While on study, all lesions (nodal and non-nodal) recorded at baseline should have their actual measurements recorded at each subsequent evaluation, even when very small (e.g., 2 mm). However, sometimes lesions or lymph nodes which are recorded as target lesions at baseline become so faint on CT scan that the radiologist may not feel comfortable assigning an exact measure and may report them as being ‘too small to measure’. When this occurs it is important that a value be recorded on the case report form:

- If it is the opinion of the radiologist that the lesion has likely disappeared, the measurement should be recorded as 0 mm. If the lesion is believed to be present and is faintly seen but too small to measure, a default value of 5 mm should be assigned and BML (below measurable limit) should be ticked (Note: It is less likely that this rule will be used for lymph nodes since they usually have a definable size when normal and are frequently surrounded by fat such as in the retroperitoneum; however, if a lymph node is believed to be present and is faintly seen but too small to measure, a default value of 5 mm should be assigned in this circumstance as well and BML should also be ticked).

This default value is derived from the 5 mm CT slice thickness (but should not be changed with varying CT slice thickness). The measurement of these lesions is potentially non-reproducible, therefore providing this default value will prevent false responses or progressions based upon measurement error.

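### Cohort 4 allows excisional biopsy of a target lesion before the first response scan, and neither the protocol nor the SAP says how a removed target lesion counts in the primary ORR

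*Protocol*

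**What the plan says.** **Method.** Protocol Table 14.2-1 makes predose and postdose biopsies mandatory in Cohort 4 unless unsafe or not feasible. Its footnote says "Excisional or punch biopsies are preferred. Core biopsies are acceptable". Attachment 2, footnote 7 repeats the preference: "For melanoma patients, excisional or punch biopsies are preferred". Cohorts 1, 2, 3 and 5 specify cores. Cohort 6 shares the melanoma footnote, but SAP 7.7 says it was never enrolled.

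**Timing.** Protocol 10.3 places the postdose biopsy in "Phase 2- Cohorts 2, 4, and 5 on Cycle 2 Day 1 only", with a window of one week either side. Protocol 10.4 schedules scans at screening and then "approximately every 8 weeks from Cycle 1 Day 1 and as clinically indicated". Protocol 10.1 puts the predose biopsy and the baseline scan in the same screening period and does not fix their order.

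**Who is biopsied on treatment.** Protocol 6.3.2.4 says "Pre- and post-dose biopsies will be collected from all patients enrolled into the Expansion phase of Cohort 4", and 10.3 and Table 14.2-1 agree. Footnote 18 of Attachment 1, and of SAP Appendix A, limits paired biopsies to the first 30 patients of Stage 2, with a predose biopsy only after that.

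**Measurability and scoring.** Entry needs "At least one tumor lesion/lymph node that meets the RECIST v1.1 criteria for measurable disease" (6.4, item 7). Attachment 4 accepts superficial skin nodules of at least 10 mm. On a lesion no longer seen it says "If it is the opinion of the radiologist that the lesion has likely disappeared, the measurement should be recorded as 0 mm", and Attachment 5, section 6 repeats this among its general measurement rules. PR is a fall of 30% or more in the sum of target diameters. SAP 7.4.1 requires confirmation at 4 weeks or later and does not mention lesions removed on study.

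**Benchmark.** Protocol 16.3 and SAP 5.3 state that 14 responders in 75 give a 95% interval whose lower limit excludes 10%.

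**The concern.** In melanoma the easiest lesion to excise may be a superficial nodule that is also a target lesion, or even the only one. If it is fully removed after the baseline scan, the next scan shows a smaller sum for a reason unrelated to treatment. ORR is a Cohort 4 primary endpoint, and for ORR this error can only add responders. The repeat scan is meant to weed out spurious responses, but a surgically removed lesion is still absent at the repeat. SAP 7.7 also moves the Cohort 4 primary endpoint from IRC to investigator assessment, so under the SAP no independent read governs it.

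**Working it through.** **1. Order of events (protocol 10.3, 10.4).** With 28-day cycles, C2D1 is Day 29, so the biopsy window is Day 29 ± 7, that is Day 22 to 36. A scan 8 weeks from C1D1 falls at about Day 57 (8 × 7 + 1). The scheduled gap is 57 − 36 = 21 days to 57 − 22 = 35 days, with the biopsy first. This is the planned order only: earlier scans are allowed, and the biopsy window can be discussed with the Medical Monitor.

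**2. Search for a rule that closes the gap.**
- *Prior local treatment* (Attachment 4) makes treated lesions non-measurable, but concerns measurability at baseline.
- *Not evaluable* (Attachment 4) covers lesions not scanned, poorly imaged or obscured. Removal is not listed.
- *Target selection* (Attachment 4) asks for large, representative, reproducibly measurable lesions. It does not exclude biopsy sites.
- *SAP Table 2* censors PFS and DOR at new cancer therapy. It does not govern ORR, and a biopsy required by the protocol is not a new therapy.
- *Cohort 4 baseline scan* (10.1) is due within 7 days before C1D1, but a scan up to 4 weeks old can replace it under stated conditions. A predose excision after the baseline scan remains possible.

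**3. Effect on the sum of diameters.** If the excised lesion carries a share s of the baseline sum and the other target lesions shrink by a fraction g, the sum falls by s + (1 − s)g. With k equal lesions, s = 1/k:

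| k | fall with g = 0 | reaches 30%? |
|---|---|---|
| 1 | 100% | yes |
| 2 | 50% | yes |
| 3 | 33% | yes |
| 4 | 25% | only if g ≥ 0.05/0.75 = 6.7% |
| 5 | 20% | only if g ≥ 0.10/0.80 = 12.5% |

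An overall PR also needs no new lesion and no non-target PD at both scans, and no progression from nadir at the second. An overall CR further needs complete response of non-target disease.

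**4. The plan's own benchmark.** The Clopper-Pearson lower limit (the SAP 7.4.1 method) is the 0.025 quantile of Beta(x, n − x + 1), with n = 75:
- x = 14: 18.7%, interval 10.60% to 29.33%. The plan's statement reproduces.
- x = 13: 17.3%, interval 9.57% to 27.81%. 10% is no longer excluded.
- x = 12: lower limit 8.55%.

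By the Wilson method, which is not the one planned, the lower limits at 14, 13 and 12 are 11.46%, 10.42% and 9.40%, so two false responses would be needed rather than one.

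**5. Possible size (assumption; the documents give no rate).** Suppose the true ORR is 10%, m patients are biopsied on treatment, and a share f of the non-responders among them is falsely scored as responding. Responders are then Binomial(75 − m, 0.10) plus Binomial(m, 0.10 + 0.90f). The probability of 14 or more is:

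| f | m = 30 | m = 66 |
|---|---|---|
| 0 | 0.016 | 0.016 |
| 2% | 0.027 | 0.048 |
| 5% | 0.054 | 0.16 |
| 10% | 0.13 | 0.48 |
| 20% | 0.41 | 0.95 |

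Here 30 comes from Attachment 1, footnote 18, and 66 is the Cohort 4 Stage 2 size in Table 22.2-1. At f = 5% the expected number of false responses is 30 × 0.9 × 0.05 = 1.35, or 66 × 0.9 × 0.05 = 2.97.

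**The case against.** The strongest reply is that the plan is silent on this case rather than wrong. Punch ranks equally with excision and core is accepted; a punch or core of a 10 mm or larger nodule normally leaves measurable tumour. In Attachment 4 the 0 mm instruction sits under lesions too faint to measure, not lesions cut out. An investigator who arranged the excision would know why the lesion is gone, and a lesion due for excision is a poor candidate for reproducible repeated measurement. All Cohort 4 patients enter while progressing, so new lesions or non-target progression will often rule out a false PR. The 14 versus 13 comparison shows only what happens at the boundary; any integer cutoff turns on one patient. The Laboratory Manual and IRC Charter were not available and may contain a rule.

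Most of this stands and limits the point. It does not remove it. Attachment 5 gives the 0 mm instruction as a general measurement rule, so a site following the text has a route to the false score and no text against it. Relying on each investigator to depart from the written rule is not prespecification. A scoring rule held only in the Laboratory Manual would still need to appear in the SAP, and the Charter would not govern an endpoint the SAP now assigns to investigators.

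A further objection is fair: carrying the pre-excision diameter forward as the primary score would make response impossible in a patient with one target lesion and could erase a real response. For that reason the non-responder count proposed here is a sensitivity analysis only.

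**Conclusion.** The gap is real and narrow. Complete excision, after the baseline scan, of a target lesion carrying about 30% or more of the baseline sum could be counted as a PR, and the 4-week repeat would not detect it provided there is no new lesion, non-target PD or other progression.

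Four stronger readings are tempting, and the documents do not support them:
- *The plan prefers excision.* It prefers excision or punch, with no ranking between them.
- *The false response is confirmed automatically.* Confirmation also requires no progression elsewhere.
- *Every error favours efficacy.* That is so for ORR. For DOR the direction is unclear, because removal also lowers the nadir against which later progression is judged.
- *The Cohort 4 ORR is materially inflated.* No frequency of target-lesion excision is given, and even the number biopsied on treatment is contradictory. The probabilities in the working rest on assumed rates.

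What can be said of size is that, by the planned interval method, one such response among 14 moves the lower limit from 10.60% to 9.57%. This is a cheap improvement that should be made, not a defect that invalidates the design.

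**What to change.** **Protocol 14.2, the Table 14.2-1 footnote and Attachment 2, footnote 7:** state that an excisional biopsy is taken from a non-target lesion and that a lesion excised predose is not selected as a target. Where no such lesion is available, the core biopsy already accepted or the existing feasibility waiver applies. Record biopsy technique and lesion identifier.

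**SAP 7.4.1:** state that surgical removal of a target lesion does not by itself count as shrinkage. List affected patients, and report a sensitivity ORR that counts as non-responders those whose response depends on the removed lesion.

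**Reconcile** protocol 6.3.2.4, 10.3 and Table 14.2-1 (postdose biopsy throughout the Cohort 4 expansion) with footnote 18 of Attachment 1 and SAP Appendix A (first 30 of Stage 2).

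The cost is a few sentences in each document and two data items. A few biopsies would become core or be waived, and the reported ORR may be slightly lower. If enrolment is complete, the lesion-selection wording comes too late, but the SAP part can still be adopted before analysis, with technique and lesion taken from biopsy records where these exist.
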